Appendix 5. Bone Scan Assessment Form

	PCCT	C Bone S	can Ass	essment	Tool	
	BASEL	INE Sca	n Date: (
Patient Identifier:						
Protocol Number:				Protocol Start Da	te:	
	ls t	tracer uptake	related to me	tastatic disease	2?	
			Yes ON , do not fill out ti			
	If yes, indica	ate total numb	er of lesions re (select one)	lated to metasta	tic disease	
	0 1	2-4	5-9	10-20	>20	
Comments				Investigator's Signature		
Version 1.0						2010, MSKCC

	8 Wee	ek Scan Date	::		
Patient Identifier:					
Protocol Number:				Start Date:	
	is tr		s No or fill out the form bel		
		Draw site(s) of NEV	V lesion(s) on skel	eton	
	orax				
□ Pe				A P	7 1
□ Ex	elvis tremities	ber of NEW lesions		dine Ssan (Date:	
□ Ex	elvis tremities		compared to Base ect one)	line Scan (Date:) ()-5
□ Ex	elvis etremities dicate total numb	2 (sel	ect one) 3 time does not confirm	4 🔘 5) ()-5
□ Ex	elvis etremities dicate total numb	2 (sel	ect one)	4 🔘 5	() (>5

PCCTC Bone Scan Assessment Tool		
Week Scan Date: (/) **To be compared to 8 Week Scan**		
Patient Identifier:	To be compared to a freeh stati	
Protocol Number:	Protocol Start Date:	
	Is tracer uptake related to metastatic disease?	
	○Yes ○No	
	NOTE: If "NO", do not fill out the form below	
	Draw site(s) of NEW lesion(s) on skeleton	
Check Region NEW Disea	• Table 1 (1) (1) (1) (1) (1) (1) (1) (1) (1) (
☐ Thora	意意 /	1
☐ Spine		1
		, \
Pelvis Extremities		
If yes, indicat	total number of NEW lesions compared to 8 Week Scan (Date:/_ (select one)	_/_)
0	O1 O2 O3 O4 O5	O>5
0	Clinical Impression (circle one) proved Stable Progression	
Comments	Investigator's Signature	
Version 1.0		2000, MSKCC

PCCTC Bone Scan Assessment Tool		
Assessment Worksheet		
Patient Identifier:		
Protocol Number:	Protocol Start Date:	
Date of Scan:	//_	
1. Are there 2 or more new lesions compared to the WEEK 8 SCAN? Yes No If YES, proceed to question 2. If NO, the patient does not have radiographic progression by bone scan.		
Is this the first scan performed POST the WEEK 8 SCAN? Yes No If YES, proceed to question 3A. If NO, proceed to question 3B.		
3A. Were there 2 or more new lesions at the WEEK 8 SCAN compared to the BASELINE SCAN? 3B. Does this scan confirm the presence of 2 or more new lesions seen since the WEEK 8 SCAN? Yes No Yes No		
If YES, patient has met conditions for radiographic progression by bone scan. If NO, the patient does not have radiographic progression by bone scan.		
Comments	Investigator's Signature	
Version 1.0 © 2010, MSKCC		

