Soft-tissue lesions: Use RECIST with caveats,

- Only report changes in lymph nodes that were ≥ 2.0 cm in diameter at baseline;
- Record changes in nodal and visceral soft tissue sites separately;
- Record complete elimination of disease at any site separately;
- Confirm favorable change with second scan.

Bone:

- Record outcome as new lesion or no new lesions

Criteria for Evidence of Radiographic Progression

Bone disease will be assessed for progressive disease only by PCWG2. The documentation required for the determination of radiographic progression is shown in the table below.

Date Progression Detected ^[1]	Criteria for Progression	Criteria to Confirm Progression	Criteria to Document Disease Progression on Confirmatory Scan
Week 9	Bone lesions: 2 or more new lesions compared to screening bone scan by PCWG2	Timing: At least 6 weeks after progression identified or at Week 16 visit ^[2]	2 or more new bone lesions on bone scan compared to Week 8 scan
	Soft tissue lesions: Progressive disease on CT or MRI by RECIST v1.1	No confirmatory scan required for soft tissue disease progression	No confirmatory scan required for soft tissue disease progression
Week 18 or later	Bone lesions: 2 or more new lesions on bone scan compared to Week 8 bone scan	Timing: At least 6 weeks after progression identified or at next imaging time point ^[2]	Persistent or increase in number of bone lesions on bone scan compared to prior scan ^[3]

Date Progression Detected ^[1]	Criteria for Progression	Criteria to Confirm Progression	Criteria to Document Disease Progression on Confirmatory Scan
	Soft tissue lesions: Progressive disease on CT or MRI by RECIST v1.1	No confirmatory scan required for soft tissue disease progression	No confirmatory scan required for soft tissue disease progression

[1] Progression detected by bone scan at an unscheduled visit either before Week 8 or between scheduled visits will require a confirmatory scan at least 6 weeks later and should follow confirmation criteria outlined in the table for the next scheduled scan.

[2] Confirmation must occur at the next available scan.

[3] For confirmation, at least 2 of the lesions first identified as new must be present at the next available scan (confirmation scan).

Disease progression in bone must be confirmed at least 6 weeks later, as per PCWG2. See table below for the timing of confirmatory imaging requirements.

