Confirmatory Imaging Requirements for Patients With CRPC Based on RECIST v1.1 and PCWG2

Disease Site	Response	Progression ^[1]
Soft tissue	Must be confirmed at least 4 weeks later	No confirmation required
Bone	Not applicable	Must be confirmed at least 6 weeks later

[1] To inform permanent treatment discontinuation.

Objective Response Status at Each Evaluation

Target Lesions	Non-target Disease	New Lesions	Objective status
CR	CR	No	CR
CR	Non-CR/Non-PD	No	PR
CR	Indeterminate or Missing	No	PR
PR	Non-CR/Non-PD, Indeterminate, or Missing	No	PR
SD	Non-CR/Non-PD, Indeterminate, or Missing	No	Stable
Indeterminate or Missing	Non-PD	No	Indeterminate
PD	Any	Yes or No, including bone determination	PD
Any	PD	Yes or No	PD
Any	Any	Yes	PD

If there is a protocol deviation and a patient has been enrolled allows enrollment of patients with only non-target disease, the following table will be used:

Objective Response Status at Each Evaluation for Patients With Non-Target Disease Only

Non-target Disease	New Lesions	Objective status
CR	No	CR
Non-CR/Non-PD	No	Non-CR/Non-PD
Indeterminate	No	Indeterminate
Unequivocal progression	Yes or No	PD
Any	Yes	PD

Procedures for Assessing PSA Response/Progression Post Study Treatment

PSA measurements will be performed on C1D1 (± 14 days) and Day 1 of Cycle 4, 7, 10 and every third cycle thereafter, as well as at the End of Treatment visit. Increases and decreases will be tracked in order to assess disease response. The PSA readings on its own will not be used to define progression in this protocol. PSA response and PSA progression will be defined according to the consensus guidelines of the PCWG2:

- PSA partial response is defined as a $\geq 50\%$ decline in PSA from Cycle 1 Day 1 (baseline) PSA value. This PSA decline must be confirmed to be sustained by a second PSA value obtained 4 or more weeks later.
- PSA progression date is defined as the date that a $\geq 25\%$ increase and an absolute increase of ≥ 2 ng/mL above the nadir is documented, which is confirmed by a second consecutive value obtained 4 or more weeks later. The first PSA reading will be obtained at week 12.

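### Read literally, the PCWG2 objective-status tables score a lone new bone lesion as progression, contradicting the same appendix's rule of two or more new lesions with confirmation

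*SAP*

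**What the plan says.** SAP 9.5 and Protocol Appendix 7 carry the same material on mCRPC response, and two parts of it bear on bone.

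**The bone rule.** The appendix states "Bone disease will be assessed for progressive disease only by PCWG2". The criterion at the first on-study scan is "Bone lesions: 2 or more new lesions compared to screening bone scan by PCWG2"; later scans also need two or more, counted against Week 8. It adds "Disease progression in bone must be confirmed at least 6 weeks later, as per PCWG2", and a footnote to the later-scan row reads "For confirmation, at least 2 of the lesions first identified as new must be present at the next available scan". The bone scan form in Protocol Appendix 5 asks "Are there 2 or more new lesions compared to the WEEK 8 SCAN"; if the answer is no, the patient has not progressed on bone scan.

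**The status tables.** The mixed-disease table assigns status from target lesions, non-target disease and a yes/no New Lesions column. Its last row is Any/Any/Yes, giving PD, with no lesion count, bone exception or cross-reference. The phrase "Yes or No, including bone determination" appears only in the row where target disease is PD. The table for patients with non-target disease only also makes any new lesion PD and does not mention bone. The bone outcome itself is captured as "Record outcome as new lesion or no new lesions".

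**The concern.** The two parts give different answers for one scan. A patient with a soft-tissue partial response and one new bone lesion has not progressed under the bone rule but is PD under the literal table. The one phrase that might link them sits where it has no effect.

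Visit-level status feeds best overall response, ORR and DOR, and the progression date used for PFS and TTP. Protocol section 2 lists response assessment by PCWG2 and RECIST 1.1 among the Part 2A and 2B primary endpoints, with ORR and the time-to-event endpoints as secondary. Bone scans in mCRPC are scheduled every 8 weeks for the first 24 weeks, on the same interval as CT/MRI, so the question can arise at every early evaluation. Protocol 7.8 bases the analysis on investigator assessments at several centres, with central review optional. Inconsistent scoring between sites would therefore pass into the results.

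**Working it through.** **Step 1. Apply both readings to one patient** (target lesions PR, non-target disease not progressing).

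| New bone lesions at the visit | Table read literally | Bone rule applied first |
|---|---|---|
| 0 | PR | PR |
| 1 | PD | PR |
| 2 or more, not yet confirmed | PD | PR (not yet PD) |
| 2 or more, confirmed | PD | PD |

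The readings differ in the two middle rows. The one-lesion row is a plain contradiction about the count. The unconfirmed row is a separate question. The confirmation table carries the footnote "To inform permanent treatment discontinuation" and does not say whether confirmation also governs status. SAP section 6 analyses PFS and TTP on unconfirmed progression.

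**Step 2. Follow a lone new bone lesion through the endpoints, with the table taken literally.**

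- *Confirmed ORR.* At the first-response scan, the visit is PD and no PR is recorded. At the confirming scan, the sequence is PR then PD, which the best-overall-response table in SAP 9.4 scores as SD or PD. Either way the confirmed response is lost.
- *Unconfirmed ORR.* SAP section 6 counts any CR or PR whether or not it is confirmed, so an earlier PR is kept.
- *Response already confirmed.* It stands, but DOR ends earlier.
- *PFS and TTP.* SAP 9.2 dates the event at the first assessment showing objective progression, and section 6 requires no confirmation, so no later step removes the event.
- *Non-target-only table.* It has no PR outcome, so what is at stake is CR status and the progression date. The plan assumes 80% of 20 Part 2B patients have measurable disease and are evaluable (16), so up to 20 − 16 = 4 could fall under this table.

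**Step 3. Illustrate the size on the planned Part 2B case** (SAP 5.2.3 and Protocol 9.6.2: 7/16 responders, threshold 30%, Uniform(0,1) prior). With r responders of 16 the posterior is Beta(1 + r, 17 − r).

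The plan prints 86.89% for 7/16. The stated prior gives P(Beta(8,10) > 0.30) = 0.895. The printed figure matches Beta(7,9), which adds no prior counts. That is a separate issue, so both scales are shown.

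| Responders | ORR | P(ORR > 30%), Uniform prior | Same, Beta(r, 16 − r) |
|---|---|---|---|
| 7 | 43.75% | 0.895 | 0.869 |
| 6 | 37.5% | 0.775 | 0.722 |
| 5 | 31.25% | 0.597 | 0.516 |

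Each responder lost costs 1/16 = 6.25 points of ORR. The number lost (0, 1 or 2) is an assumption; the documents give no rate of lone new bone lesions among responders.

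**The case against.** The strongest reply is that the appendix already settles the matter. The sentence "Bone disease will be assessed for progressive disease only by PCWG2" comes before the status table, and investigators complete a bone form that requires two lesions. The table's phrase about bone determination suggests that the result of the PCWG2 assessment, not a raw count, enters the column. No text says that the recorded bone outcome is the entry for that column; the link is an inference from matching yes/no wording. Status is investigator-provided, so nothing shows that it is programmed mechanically from the table.

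Much of this stands. A reader might infer that the plan definitely scores one new bone lesion as PD, and the documents do not support that: a careful analyst could apply the bone rule first. But the table does not tell anyone to do so, and its bone phrase is in a row it cannot affect. The RECIST text in Protocol Appendix 6 and SAP 9.4 points the other way, since any new unequivocal malignant lesion is PD.

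Two further limits are fair. The remark that bone lesions may reflect trauma or flare belongs to the eligibility text, so it is not evidence about on-study scans. Requiring confirmation would largely remove lone-lesion PFS events, because a single lesion cannot meet the confirmation criteria; but section 6 does not require it for PFS or TTP. Finally, no formal decision hangs on P(ORR > 30%), as SAP 5.1 states no hypotheses.

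**Conclusion.** The point holds as a contradiction between two stated rules in the same appendix, repeated in protocol and SAP. The literal table misclassifies a lone new bone lesion against the appendix's own bone rule. If it is applied that way, confirmed ORR, DOR, PFS and TTP can all change.

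A reader might go further and conclude that one bone lesion cancels any soft-tissue response, or that ORR and PFS are certainly biased downward. Neither follows. An earlier PR stays in the unconfirmed ORR, an already confirmed response stays a response, and the effect arises only where the table is applied literally.

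The size is unknown. The shift from 43.75% to 37.5% or 31.25% assumes 1 or 2 of 7 responders affected at the first-response or confirming scan; with none affected there is no change in ORR. This should be corrected before Part 2 responses are derived.

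**What to change.** In both status tables of SAP 9.5 and Protocol Appendix 7:

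1. Define New Lesions = Yes for mCRPC as a new unequivocal soft-tissue lesion by RECIST 1.1, or bone progression meeting the appendix's PCWG2 rule of two or more new lesions. A lone new bone lesion is then No.
2. Move the bone qualifier from the target-PD row to the Any/Any/Yes row, and add it to the matching row of the non-target-only table.
3. State separately whether two or more new bone lesions not yet confirmed count as PD in the unconfirmed PFS, TTP and DOR analyses, reconciling SAP section 6 with the PCWG2 confirmation rule. This is an analysis decision in its own right: coding such lesions as No would turn the stated unconfirmed analysis into a confirmed one for bone.
4. Where bone progression is later confirmed, date it to the first scan. Protocol Appendix 6 and SAP 9.4 already do this for equivocal new lesions.

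The cost is wording in two documents and a programming rule. No scans are added and no rule on patient management changes. The downside is that some visit statuses stay provisional until the next bone scan.

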4.1. Inclusion Criteria

Patients must meet all of the following inclusion criteria to be eligible for enrollment in the study:

- 1. For Part 1A (monotherapy dose escalation phase): Histological or cytological diagnosis of a solid tumor that is advanced/metastatic, patients are intolerant to standard treatment, resistant to standard therapy or for which no standard therapy is available for the following tumor types:
 - Breast cancer;
 - Prostate cancer (mCRPC testosterone less than 50 ng/dL);
 - Squamous cell cancer of the head and neck;
 - Melanoma;
 - Mesothelioma;
 - Pancreatic cancer;
 - Colorectal cancer;
 - Renal cell carcinoma;
 - Hepatocellular cancer.

2. For Part 1B (Combination Dose Escalation Phase): histological or cytological diagnosis of mCRPC (castration is defined as having a serum testosterone less than 50 ng/dL due to medical or surgical castration), patients who are intolerant to standard treatment, resistant to standard therapy, or refuse to standard therapy.

3. Part 2A and Part 2B:

- Histologically or cytologically confirmed prostate adenocarcinoma metastatic disease.
- Effective castration with serum testosterone levels <0.5 ng/mL (1.7 nmol/L).
- Having received 3 or more cycles of prior docetaxel therapy (before or after abiraterone).
- Having PD while receiving abiraterone acetate within 12 months of abiraterone treatment initiation (≤12 months).
- Progressive disease (PD) by:
 - a. Progression in measurable disease per RECIST 1.1 criteria. Patient with measurable disease must have at least 1 lesion that can be accurately measured in at least 1 dimension (longest diameter to be recorded). Each lesion must be at least 10 mm when measured by computed tomography (CT) (CT scan thickness no greater than 5 mm) or magnetic resonance imaging (MRI). Lymph nodes should be ≥15 mm in short axis. As defined by PCWG2, if lymph node metastasis is the only evidence of metastasis, it must be ≥20 mm in diameter when measured by spiral CT or MRI. Previously irradiated lesions, primary prostate lesion, and bone lesions will be considered non-measurable disease, or
 - b. Appearance of 2 or more new bone lesions (PCWG2). They must be confirmed by other imaging modalities (CT; MRI) if ambiguous results, or

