 - c. Rising PSA defined (PCWG2) as at least 2 consecutive rises in PSA to be documented over a reference value (measure 1) taken at least 1 week apart. The first rising PSA (measure 2) should be taken at least 7 days after the reference value. A third confirmatory PSA measure is required (second beyond the reference level) to be greater than the second measure and it must be obtained at least 7 days after the second measure. If this is not the case, a fourth PSA measure is required to be taken and be greater than the second measure. The third (or the fourth) confirmatory PSA should be taken within 4 weeks prior to enrollment. A PSA value of at least 2 ng/mL is required at study entry.
- Prior abiraterone acetate must be stopped at least 2 weeks before study treatment.

- 4. Patients must have recently obtained archival tumor tissue available for submission to the sponsor (except for Part 2A monotherapy dose expansion). Patients enrolled in Part 1 and Part 2 should have access to their archival formalin-fixed paraffinembedded material, collected within 6 months of screening, containing tumor that is of diagnostic quality and representative of their diagnosed malignancy or whenever possible, consent to undergo a biopsy during screening. The sponsor should be contacted if obtaining a new biopsy is not medically feasible for approval to enroll, prior to initiating screening activities.
- 5. Patients entering the study in the subgroup(s) requiring mandatory pre- and on-treatment tumor biopsies in Part 2A and 2B must have a tumor amenable to biopsy and consent to these planned biopsy procedures. The sponsor should be contacted if obtaining a pre-treatment and on treatment biopsies is not medically feasible for approval to enroll, prior to initiating screening activities.
- 6. Age \geq 18 years.
- 7. Eastern Cooperative Oncology Group (ECOG) Performance Status (PS) 0 or 1.
- 8. Adequate bone marrow function (see Appendix 3), including:
 - Absolute Neutrophil Count (ANC) $\geq 1,500/\text{mm}^3$ or $\geq 1.5 \times 10^9/\text{L}$;
 - Platelets $\ge 100,000/\text{mm}^3 \text{ or } \ge 100 \text{ x } 10^9/\text{L}$;
 - Hemoglobin ≥9 g/dL.
- 9. Adequate renal function, including serum creatinine ≤1.5 x upper limit of normal (ULN) or estimated creatinine clearance ≥60 mL/min as calculated using the method standard for the institution. In equivocal cases, a 24-hour urine collection test can be used to estimate the creatinine clearance more accurately.

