All sites of disease must be assessed at baseline. Baseline assessments should be done as close as possible prior to study start. For an adequate baseline assessment, all required scans must be done within 28 days prior to treatment and all disease must be documented appropriately. If baseline assessment is inadequate, subsequent statuses generally should be indeterminate.

Target lesions

All measurable lesions up to a maximum of 2 lesions per organ, 5 lesions in total, representative of all involved organs, should be identified as target lesions at baseline. Target lesions should be selected on the basis of size (longest lesions) and suitability for accurate repeated measurements. Record the longest diameter for each lesion, except in the case of pathological lymph nodes for which the short axis should be recorded. The sum of the diameters (longest for non-nodal lesions, short axis for nodal lesions) for all target lesions at baseline will be the basis for comparison to assessments performed on study.

- If 2 target lesions coalesce the measurement of the coalesced mass is used. If a large target lesion splits, the sum of the parts is used;
- Measurements for target lesions that become small should continue to be recorded. If a target lesion becomes too small to measure, 0 mm should be recorded if the lesion is considered to have disappeared; otherwise a default value of 5 mm should be recorded.

NOTE: When nodal lesions decrease to <10 mm (normal), the actual measurement should still be recorded.

Non-target disease

All non-measurable disease is non-target. All measurable lesions not identified as target lesions are also included as non-target disease. Measurements are not required but rather assessments will be expressed as ABSENT, INDETERMINATE, PRESENT/NOT INCREASED, INCREASED. Multiple non-target lesions in one organ may be recorded as a single item on the CRF (eg, 'multiple enlarged pelvic lymph nodes' or 'multiple liver metastases').

OBJECTIVE RESPONSE STATUS AT EACH EVALUATION.

Disease sites must be assessed using the same technique as baseline, including consistent administration of contrast and timing of scanning. If a change needs to be made the case must be discussed with the radiologist to determine if substitution is possible. If not, subsequent objective statuses are indeterminate.

Target disease

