5.3.2. Analyses for Binary Data

Binary endpoints in this study include ORR, complete response (CR), and partial response (PR). Response assessment will be based on PCWG2 for prostate cancer patient, and will use RECIST 1.1 for other tumor types. If deemed necessary disease control rate (ie, DCR, which is defined as the proportion of patients that achieved CR, or PR, or stable disease) may also be calculated for Part 2. Descriptive statistics along with the corresponding 2-sided 95% confidence intervals using an exact method will be provided for these endpoints.

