9.5. Prostate Cancer Working Group 2 (PCWG2) – Soft Tissue Response Criteria

Adapted from Scher H.I., et al: Design and End Points of Clinical Trials for Patients with Progressive Prostate Cancer and Castrate Levels of Testosterone: Recommendations of the Prostate Cancer Clinical Trials Working Group. *J Clin Oncol.* 26 (2008) 1148-1159.

[figure not shown]
And Eisenhauer E.A., et al: New response evaluation criteria in solid tumors: Revised RECIST guideline (version 1.1). *European Journal of Cancer* 45 (2009) 228–247.

Evidence of PD to Determine CRPC Eligibility

Patients being considered for trial entry should have evidence of disease progression by either PSA, RECIST, or bone scan to be eligible.

PSA: PSA evidence of disease progression based on the prostate cancer working group (PCWG) 2 criteria consist of a minimum PSA level 2.0 ng/ml that has risen on at least 2 successive occasions, at least 1 week apart. The reference value #1 is the last value before the rise in PSA was observed. If the confirmatory PSA value (Figure 2, #3A) is greater than the screening value then progression by PSA is met and the patient is eligible for trial enrollment on the basis of PSA alone. If the confirmatory PSA (Figure 2, #3B) value is less than the screening PSA (Figure 2, #2) value, then an additional test for rising PSA (#4) will be required to document progression before the patient can be enrolled.

Figure 2. Change in PSA

Target lesion/measurable disease: Patients are not required to have evidence of disease progression by measurable disease if they meet the criteria for disease progression on the basis of PSA or bone scan. Evidence of nodal or visceral disease RECIST 1.1 progression however is sufficient for trial entry independent of PSA readings. Because lymph nodes may be enlarged due to benign pathology, only lymph nodes that are ≥ 2.0 cm should be used for disease evaluation.

Bone scan: Evidence of disease progression based on bone scan appearance is sufficient for trial entry independent of PSA readings. If the appearance of the bone scan is the only indicator of progression, then there must be ≥ 2 new bone lesions compared with the prior bone scans. If there is ambiguity about the appearance of the bony lesions such as traumatic in nature or secondary to a flare reaction, then it is recommended that an alternative imaging modality such as MRI or fine-cut CT be used to evaluate these lesions further.

CRITERIA FOR OUTCOME MEASURES:

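### The status table for patients with only non-target disease applies only after a protocol deviation, although such patients are eligible; read literally, their non-progressing visits are Indeterminate or unclassified

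*SAP*

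**What the plan says.** **Eligibility.** Protocol 4.1, Inclusion 3, offers three routes to documented progression in Parts 2A and 2B, joined by *or*: measurable disease, bone scan or PSA. The bone route begins "Appearance of 2 or more new bone lesions (PCWG2", and the PSA route "Rising PSA defined (PCWG2) as at least 2 consecutive rises in PSA". The demand for a measurable lesion is conditional: "Patient with measurable disease must have at least 1 lesion that can be accurately measured in at least 1 dimension". SAP 9.5 and Protocol Appendix 7 agree: "Patients are not required to have evidence of disease progression by measurable disease" when PSA or bone scan already shows it.

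**How such disease is classed.** Inclusion 3 says "Previously irradiated lesions, primary prostate lesion, and bone lesions will be considered non-measurable disease". Protocol Appendix 6 adds "All non-measurable disease is non-target".

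**Status tables.** SAP 9.5 and Protocol Appendix 7 print a main objective-status table, indexed by target status, non-target status and new lesions. A second table follows for patients with non-target disease only. In both documents the second is introduced by "If there is a protocol deviation and a patient has been enrolled allows enrollment of patients with only non-target disease".

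**Sizing.** SAP 5.2.3 and Protocol 9.6.2 assume that 80% of the 20 Part 2B patients have measurable disease and are response evaluable, giving 16.

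**Disease control rate (DCR).** SAP 5.3.2 allows a DCR for Part 2 if deemed necessary, "which is defined as the proportion of patients that achieved CR, or PR, or stable disease".

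**The concern.** The second table is conditioned on an event that need not have happened. Having only non-target disease is allowed by the inclusion criteria and foreseen in the sizing text, so it is not a deviation. If the condition is applied as printed, the table written for these patients is withheld from them and they are classified by a table built around target lesions.

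The main stake is best overall response. A fully scanned patient whose bone disease has not progressed would be reported as though the assessment had failed. Both documents assess bone for progression only, so absence of progression is the informative favourable outcome for this group, and the printed rule hides it.

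**Working it through.** **Step 1: the plan's own figure.** 0.80 × 20 = 16, as printed. The remainder is 20 − 16 = 4. Because the 16 must be both measurable and evaluable, some of the 4 may have measurable disease but be unevaluable. So 4 of 20 is an upper figure for Part 2B patients without target lesions. No share is given for Part 2A. If 10% to 50% of its 10 patients lacked measurable disease (an assumption), that is 1 to 5 patients.

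**Step 2: is a patient without target lesions eligible?** Routes b and c of Inclusion 3 need no measurable progression, and no other item requires a measurable lesion of everyone. Bone lesions are non-measurable and therefore non-target. A bone-only patient thus has no target lesion, unless a bone lesion has a measurable soft-tissue component (Appendix 6). Entry by bone scan or PSA does not imply absence of target lesions; it permits it. Inclusion 1 (Part 1A) and Inclusion 2 (Part 1B) do not require measurable disease either, and their prostate cancer patients are also assessed by PCWG2.

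**Step 3: look up each visit in both tables, with no target lesions.**

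| Non-target finding | Main table | Non-target-only table |
|---|---|---|
| CR, no new lesion | Indeterminate, or no row | CR |
| Non-CR/Non-PD, no new lesion | Indeterminate, or no row | Non-CR/Non-PD |
| Indeterminate, no new lesion | Indeterminate, or no row | Indeterminate |
| Progression, or a new lesion | PD | PD |

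The main table has only one non-progression row whose target status is not CR, PR or SD. It takes target status Indeterminate or Missing with non-target Non-PD, and returns Indeterminate. Whether Missing includes having no target lesions at baseline is not stated. If it does not, no non-progression row fits.

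**Step 4: which endpoints move.**
- *Best overall response:* moves directly, through the first two rows.
- *ORR:* moves only in the first row. Response in bone is marked not applicable, so a bone-only patient is a non-responder under either table. Appendix 6 also requires tumor marker normalization for a non-target CR.
- *DCR:* neither Indeterminate nor Non-CR/Non-PD is CR, PR or stable disease. Changing the trigger alone leaves DCR unchanged, apart from a non-target CR. The separate exposure under the DCR definition is at most 4/20 = 20 percentage points, if all 4 lack target lesions and all have disease control.

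**The case against.** The strongest reply is that the trigger sentence is garbled. It reads like two alternatives run together, one for a deviation and one for a protocol that permits such patients. The table's title refers simply to patients with non-target disease only, so a sensible programmer would use it for them. This has force, but the printed condition is still a deviation, in both documents, and two programmers could reasonably choose differently.

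Second, Appendix 6 defines Indeterminate for target lesions that exist but were not properly assessed, or were excised or irradiated. It does not describe a patient who has none. That stands, and is why the result is stated as Indeterminate or no matching row. Either way the patient lacks a correct status.

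Third, the practical reach is limited. Response is investigator-provided, PSA50 (a primary efficacy endpoint of Part 2 in the protocol) is untouched, and the SAP tests no hypotheses. This also stands and limits the weight of the point.

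A reader might infer three stronger conclusions that the documents do not support:

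- *That these patients' PFS is censored at the first dose.* This needs a performed but Indeterminate scan to count as missed or as no assessment. SAP 9.2 does not say so; it is silent on whether an Indeterminate visit is an objective assessment. Any count of lost events would also need a median PFS that neither document gives.
- *That eligible patients would be recorded as deviations.* SAP 4.8 leaves that to the sponsor's procedures, with the list settled before database release. A table's introductory sentence does not decide it.
- *That the trigger causes a 20-point loss in DCR.* That loss comes from the DCR definition and persists under either table.

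**Conclusion.** The trigger contradicts the eligibility criteria in both documents and is wrong as written. On its literal reading, an eligible patient without target lesions has no correct status at any assessable visit without progression. The effect falls on best overall response, and on ORR only for a non-target CR, which should be uncommon. In Part 2B it concerns at most 4 of 20 patients on the plan's 80% assumption. It extends to Part 2A and to PCWG2-assessed patients in Part 1, where the plan gives no share.

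The DCR question is separate: an optional endpoint, at most 20 points, driven by its definition. For PFS and time to progression the SAP leaves a rule unstated; no loss of events is shown. The conclusion rests on reading the printed condition literally. If the sentence was meant to cover protocols that permit such patients, the intention was right and only the wording fails.

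**What to change.** 1. In SAP 9.5 and Protocol Appendix 7, replace the introductory sentence with: *For patients with no target lesions at baseline (any Part, assessed by PCWG2), the following table is used.* Tying it to Inclusion 3 alone would omit Parts 1A and 1B.
2. In SAP 9.2, state that a Non-CR/Non-PD visit is an objective tumor assessment without progression, which settles the censoring rule for these patients.
3. Separately, if DCR is reported, state in SAP 5.3.2 that Non-CR/Non-PD counts as disease control.

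The first two items need only wording and programming, with no new data and no change to patient management. The third has a modest cost: the status tables keep Stable and Non-CR/Non-PD distinct, so combining them broadens what DCR measures. Showing the two counts separately beside the rate would keep that visible.
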